Design overview. Groups of 3-5 clinicians were recruited by each agency leader. Once all clinicians at an agency were enrolled, they had a 2-week initial training period in which they completed the Project ImPACT Beginner e-Course, a 6-hour self-directed online tutorial on Project ImPACT intervention content. The Beginner e-Course consisted of didactic modules with slides and audio recordings about Project ImPACT NDBI intervention strategies and best practices for collaborating with parents. Modules included video examples of caregivers implementing the intervention strategies and periodic quizzes about course content, but did not include explicit instruction about parent coaching.

Following the initial training period, clinicians entered the Baseline Phase (3 to 9 weeks; randomized by agency) during which they were asked to follow the Project ImPACT coaching manual and meet weekly with their enrolled families, but did not receive consultation support. After the baseline phase, all enrolled clinicians at each agency entered the consultation phase, during which they received 12 group consultation sessions, once per week, for 1.5 hours per session. The consultation phase included three, 4-week blocks in which the group completed one consultation training activity per block (i.e., case support, skill rehearsal, or feedback on

videotaped sessions). Clinicians submitted recordings of all Project ImPACT telehealth sessions throughout the Baseline and Consultation phases, and then again at Follow Up (8-weeks post consultation). Information about the procedures used in each phase is outlined below.

Baseline phase. Clinicians received an e-book copy of the Project ImPACT Coaching Manual, which includes detailed descriptions about the theoretical underpinnings of the intervention and lesson plans for each of the 24 sessions (e.g., session agendas, handouts, access to video models of NDBI intervention strategies, examples of trouble-shooting tips for common challenges with clients). Clinicians also received an e-book copy of the Project ImPACT Parent Manual, which includes descriptions of the NDBI strategies in parent-friendly language and tips about how to apply NDBI strategies at home and in the community. Clinicians were instructed to follow the lesson plans in the Project ImPACT coach manual and no consultation support was provided during the Baseline phase.

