Methodological challenge with the baseline phase. The research team became aware of a methodological flaw following visual analysis of manual adherence data from the first 4 agencies. Within-condition visual analysis indicated that baselines across agencies were unstable due to inflation of the manual adherence scores for the first 2 sessions of Project ImPACT, as compared to sessions 3-24. Conceptually, this made sense because these 2 sessions were atypical and did not include instruction on NDBI techniques nor an active parent coaching component in which clinicians provided feedback; session 1 was an overview of the program and session 2 was a goal setting session. Both sessions are much less complex than the other parent coaching sessions. Agencies #1-4 had started data collection by this point, and due to the initial randomization procedure using parameters of 3-6 weeks of baseline, only 1 agency had at least 3 weeks of usable baseline sessions (Agency #2). For this reason, an additional 2 agencies were recruited (Agencies #5 and #6), and baseline lengths for those agencies were randomized for 6-9 weeks to ensure that baseline lengths had at least 3 usable Project ImPACT sessions. Additionally, to allow for the retention of all clinicians in Agencies #5 and #6, baselines for those two agencies were extended by 1 week to allow for clinicians who had multiple cancellations in the baseline period to acquire at least 2 usable baseline sessions.

Consultant Fidelity to Consultation Conditions

Consultant fidelity to the three consultation conditions was assessed by 2 coders naïve to condition and timepoint using the Project ImPACT Consultation Adherence Checklist. The checklist included scores for the percentage of required training activities for each of the 3 consultation components, as well as the length of time spent on the training activities (e.g., time

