mediated interventions (e.g., providing effective in-vivo corrective feedback to caregivers, problem-solving challenges with between-session practice). Subscales included: Collaboration, Demonstration, In-Vivo Feedback, and Reflection and Problem-Solving. Clinically, a score of 4 or 5 for each subscale would be considered “at fidelity.” As this measure is relatively new, no psychometric data has been published yet. All Project ImPACT sessions were randomly assigned to be scored for parent coaching competency by one primary coder naïve to timepoint and condition. Coders needed to meet training criteria of 3 videos in a row with 90% of items within one point of the master codes prior to coding for the actual dataset. Monthly meetings with the coding team were held in which all members independently coded a video, and the group compared their scores to the master codes and discussed discrepancies. Twenty-five percent of Project ImPACT sessions were scored by a second independent coder for reliability. Intra-class correlations ranged from 0.63 to 0.99, indicating moderate to excellent reliability; see Table 7 for all ICCs.

Table 7. Intra-class correlations for each PEACE subscale.

Subscale	Intra-class Correlation
Collaboration	0.69
Demonstration	0.79
In-Vivo Feedback	0.99
Reflection and Problem-Solving	0.63

Data Collection for Questionnaires

During the consultation period, clinicians completed weekly online questionnaires about the following: cancellations/rescheduling information, case penetration (Penetrability Formula), perceptions about Project ImPACT (Perceived Characteristics of Intervention Scale), and perceptions on the usability of that week's consultation training activity (Implementation Strategy Usability Scale). No clinician questionnaires were collected during the 8-week follow up period. After the follow up period, clinicians submitted a final recorded session and set of questionnaires.

Caregivers completed a caregiver-report questionnaire about autism-related challenges (Autism Impact Measure) via online questionnaire at 5 time points: at intake, at the end of each consultation condition (i.e., 4-, 8-, and 12-weeks into the consultation phase), and at the end of the 8-week follow up period.

Measures

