Statistical Analysis. An overview the statistical analysis used for each aim is presented in this section. Recent advances in statistical modeling have resulted in the specification of multilevel models that can provide effect sizes for each treatment element while also accounting for the specific features of single-case experimental designs (e.g., handling auto-correlation among consecutive datapoints, correcting for design-specific error structures). These advances have resulted in statistical packages in the R statistics platform (e.g., *sdhlm*). These tools were used to analyze results for Aims 1, 3, and 4. Specific model parameters are presented in the Results section.

Multilevel modeling for Aim 1: Effects of the group consultation model and each consultation component on clinician manual adherence and parent coaching competency. Only data from the 3 agencies with sufficient baseline data were used for Aim 1 analysis. We examined the effects of individual components of the group consultation model (i.e., consultation training activities) on clinician fidelity (i.e., manual adherence, parent coaching competency). To do so, we utilized 2-level multilevel models to estimate the change in level from the average baseline fidelity score to the average fidelity level for each consultation training activity condition (i.e., changes in level from baseline to each consultation condition). For example, the model estimated the magnitude of change from the Baseline level to the Feedback level, and whether the change was statistically significant. Specific model parameters for all models are presented in the Results section.

The models provide two sets of estimates: 1) the average effect of each consultation component on fidelity scores *averaged across clinicians* (i.e., results from the 2-level model),

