and 2) *participant-specific* parameter estimates that demonstrate the effect of consultation components on an individual clinician's fidelity scores. First, estimates for the 2-level model (averaging across clinicians) include estimated fixed effects for each consultation component and random deviations for each clinician. These deviations are obtained from the random effect estimates, which included an intercept for each clinician and a random component for each of the 3 consultation phases. These random effects for the intercept allow the model to vary for each clinician in regard to their baseline fidelity level. The random effects for each consultation component allowed for the estimated effects of each consultation component to vary across clinicians (e.g., the effect of feedback could have a stronger magnitude for clinician 0201 than 0502). Next, the participant-specific parameters are estimated using the fixed and random effect estimates from the 2-level model. They are a combination of fixed effects and the between-participant variance. These participant-specific parameters quantify the effects of each consultation component on an individual clinician's fidelity levels. However, the model does not compute tests of statistical significance for effects of each consultation component on individual clinicians. In order to test whether the observed effects were statistically significant for a given clinician, one would need to fit separate multilevel models for each of the 5 outcome variables for each clinician (a total of 60 separate models), which was beyond the scope of this project. Also, those separate individual multilevel models would not account for between-participant variation, which is a major strength of the two-level multilevel models used in this analysis. Although we hoped to include a third level of nesting (i.e., agency-level effects such as how the rurality of agency #1 affects estimates), our sample size was too small to do so.

Aim 2: Relative usability of each consultation component. We examined statistical differences among mean ratings of each consultation component (i.e., training activity) on the

Implementation Strategy Usability Scale. Usability ratings were averaged for each consultation condition for each clinician and then examined using a repeated measures one-way ANOVA. Questionnaires from all 6 agencies were utilized for this analysis.

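### Uncertainty for clinician-specific effects in Aim 1 does not require 60 further models: the five two-level models already determine it, and the plan mentions no measure of it

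*Combined protocol and SAP*

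**What the plan says.** The point is in the Combined protocol and SAP, under Statistical Analysis, Multilevel modeling for Aim 1. The two-level model has fixed effects for the three consultation components and, as random effects, "an intercept for each clinician and a random component for each of the 3 consultation phases". Two sets of estimates come from it: effects averaged over clinicians, and participant-specific effects computed from the fixed and random parts. Of the second set the plan says "They are a combination of fixed effects and the between-participant variance", and it presents them as quantifying each component's effect on an individual clinician's fidelity.

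The plan then says that the model gives no significance test for a single clinician. To obtain one, "one would need to fit separate multilevel models for each of the 5 outcome variables for each clinician". It puts the number at 60 and regards that work as more than the project could take on. It adds that separate models would lose the between-clinician information that is a strength of the two-level model. It mentions no standard error, interval or other measure of uncertainty for the participant-specific effects. Detailed model parameters are left to a Results section that is not part of the documents.

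**The concern.** The plan treats clinician-level inference as something that the fitted model cannot supply. That is incorrect. In a linear mixed model, the variance of the prediction error for each clinician's effect follows from the fit itself. The alternative that the plan names is also the weaker one: a model of one clinician's sessions has no clinician level, so it is a single-level regression that borrows nothing from the other clinicians.

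What is at stake is how one of the two declared sets of estimates can be read. Data per clinician and phase are thin. Each component block lasts 4 weeks, 25.4% of scheduled sessions in the three analysed agencies were cancelled, and two agencies' baselines were extended so that clinicians with several cancellations could manage "to acquire at least 2 usable baseline sessions". With so few sessions, two clinicians' estimates can differ noticeably by chance, and point values alone give the reader no way to judge that.

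**Working it through.** **1. The plan's figure.** There are five outcomes: manual adherence plus four PEACE competency scores ("Subscales included: Collaboration, Demonstration, In-Vivo Feedback, and Reflection and Problem-Solving"). On clinicians, "Only data from the 3 agencies with sufficient baseline data were used for Aim 1 analysis" and "Groups of 3-5 clinicians were recruited by each agency leader", so 9 to 15 clinicians and 45 to 75 models are possible. The stated 60 implies 60 / 5 = 12 clinicians, which is inside that range. The count reproduces.

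**2. Models actually needed.** For clinician i, let b be the estimated fixed effects with covariance C, D the random-effect covariance, X the phase design and V = X D X' + R, where R is the residual covariance.
- Clinician-specific effect: b + u_i, with u_i = D X' V^-1 (y_i - X b).
- Prediction-error variance: M C M' + D - D X' V^-1 X D, with M = I - D X' V^-1 X.

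Every term comes from the fit already made. Five fits give 12 x 3 x 5 = 180 clinician-by-component effects, each with a prediction variance, and no additional model. This does not depend on any assumed variance.

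**3. Illustrative size.** The documents give no variances. Assume a within-clinician SD of 10 adherence points, independent errors and, for now, no fixed-effect error.
- Raw contrast, 3 baseline and 3 component sessions: variance 100 x (1/3 + 1/3) = 66.7; 95% half-width 1.96 x 10 x sqrt(1/3 + 1/3) = 16.0 points. With 2 baseline sessions: 1.96 x 10 x sqrt(1/2 + 1/3) = 17.9. With 6 baseline and 4 component sessions: 1.96 x 10 x sqrt(1/6 + 1/4) = 12.7. The plan does not use this raw estimator; it is the reference for shrinkage.
- After shrinkage, 3 + 3 sessions, between-clinician SD tau of the effect: conditional SD = 1 / sqrt(1/tau^2 + 1/66.7), which is 4.3 for tau = 5 and 6.3 for tau = 10. Half-widths are 8.4 and 12.4 points.

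**4. Simulation of the two-level model.** The settings were 12 clinicians, residual SD 10, intercept SD 8, diagonal D, independent errors, REML and 100 runs per row. Widths are full 95% widths in points and include fixed-effect error.

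| tau | Sessions (baseline + per component) | Plug-in width | Plug-in coverage | Width if variances known | Separate per-clinician width | Runs with a variance component near zero |
|---|---|---|---|---|---|---|
| 3 | 6 + 4 | 11.2 | 85% | 12.4 | 27.0 | 78% |
| 6 | 6 + 4 | 15.8 | 88% | 17.3 | 27.4 | 26% |
| 10 | 6 + 4 | 19.6 | 92% | 20.6 | 27.3 | 3% |
| 6 | 3 + 3 | 17.0 | 86% | 19.3 | 36.5 | 33% |

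Two results follow. The two-level model is more precise than separate models, even judged by the known-variance widths (12.4 to 20.6 against about 27 with 6 + 4 sessions). But simple plug-in intervals are too narrow with about 12 clinicians, because they treat the variance components as known.

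**5. Range.** Steps 3 and 4 together give shrunken half-widths from about 6 points (12.4 / 2 = 6.2) to about 12 points (12.4). Widths scale with the SDs. If all SDs were halved, the range would be about 3 to 6; if multiplied by 1.5, about 9 to 19.

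**The case against.** The plan is open about the absence of individual tests, and it rejects separate models for a sound reason: they discard between-clinician variation. In practice it kept the better estimator, shrunken effects from one joint model. Only the reason given is wrong. This stands, and it limits the point to a correction of the statement plus added reporting for a secondary output.

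Three stronger readings are tempting, and the documents do not support them.
- A reader might infer that the participant-specific effects were reported as bare point values. The text says only that significance tests are not computed. The Results section is not available, so what was reported is unknown; one can say only that no uncertainty measure is mentioned here.
- A reader might infer that the estimates are used to show which clinicians benefited. The one comparison of two named clinician codes is a hypothetical that explains random effects. No clinician is classified and no decision rests on these values.
- A reader might infer that the Aim 1 conclusions are weakened. Those rest on the average fixed effects and on agency-level visual analysis with replication across three agencies.

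It can also be said that intervals bring their own problems. This is partly right. Plug-in intervals under-cover, and a rule that calls a clinician improved when the interval excludes zero would amount to about 180 uncorrected tests. At 85% to 92% coverage, roughly 27 to 14 of 180 intervals would miss their true value. Where a component's between-clinician variance collapses to zero, all clinicians receive the same estimated effect, so such a rule would only restate the group mean. These are reasons to choose the interval method with care and to omit any classification rule. They are not reasons to leave the intervals out.

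**Conclusion.** The point holds in a limited form. The statement that clinician-level inference requires 60 separate models is technically wrong: the five two-level models already determine a prediction variance for every participant-specific effect. The plan mentions no uncertainty measure for these estimates, although it presents them as quantifying effects for individual clinicians. That conclusion follows from the model's structure and needs no assumption.

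The size is illustrative. Half-widths of about 6 to 12 adherence points rest on an assumed within-clinician SD of 10, a between-clinician effect SD of 3 to 10, 3 to 6 baseline and 3 to 4 component sessions, and independent errors. The clinician number of 12 is implied by the plan's 60. Nothing is computed for the four competency subscales, which use a 5-point scale. The matter is minor: it concerns a secondary, descriptive output.

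**What to change.** Delete the statement about 60 models. State instead that each participant-specific effect is the fixed effect plus the clinician's predicted deviation, and report it with a 95% prediction interval from the two-level model. The interval should allow for uncertainty in the variance components and for the autocorrelation in the fitted model, through a parametric bootstrap or a Bayesian fit with weakly informative priors; plug-in conditional variances alone are not enough. Present the intervals descriptively, without a rule that labels clinicians as improved. Note each component and outcome for which the between-clinician variance is estimated near zero, since the individual effects there mostly repeat the average.

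The cost is modest extra computation on existing data and models. The downside is that the intervals will be wide and the individual results will look less definite.

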Baseline lengths were randomized by a statistician unaware of agency characteristics using a random-number generator. Published standards for single-case designs require a minimum of 3 observations per phase to “meet standards with reservations” (Kratochwill et al., 2013). See Table 2 for the baseline lengths for each agency. Baseline lengths for agencies 1-4 were randomized for 3-6 weeks. Due to a methodological challenge (outlined below), baseline lengths for agencies #5 and #6 were randomized for 6-9 weeks to ensure that clinicians had sufficient baselines.

Consultation phase. Group consultation sessions took place via a teleconference platform (Zoom). During a given consultation condition (i.e., 4-week block in which only one consultation training activity was delivered), no components of any other conditions were provided. For example, during the skill rehearsal condition, no feedback was given about the role

plays, so that the only performance feedback clinicians received occurred in the feedback condition. All providers received each of the 3 consultation conditions (i.e., training activities), with each training activity delivered in isolation for a given 4-week consultation period. The order in which providers received each component was randomized for each agency by a statistician unaware of agency characteristics using a random-number generator, such that each agency had an equal chance of receiving one of the predetermined permutations of conditions (e.g., equally as likely to be randomized to ABCD order as ADCB order). Consultation sessions were rescheduled for the following week if more than half of participants at an agency would not be present or if the consultant would not be present. See Table 2 for the consultation component order for each agency.

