spent in role plays). This measure has not been empirically tested, but was used to understand the level of experimental control in the study (i.e., extent to which only one consultation component was delivered in a given phase). Items were rated as Observed (1), Not Observed (0), or Not Applicable. Example items for the Feedback condition include: consultant asked each trainee to introduce their clip prior to screensharing it, consultant prompted each trainee to provide specific praise/constructive feedback about each clip shown, consultant provided specific praise/constructive feedback after each clip. Example items for the Skill Rehearsal condition include: each trainee present at the session completed at least 1 role play scene, consultant asked trainees to self-reflect on clinician performance in role play scenes using the reflection worksheet, scene A was completed. Example items for the Case Support condition include: consultant asked the group of trainees to provide potential solutions to the implementation challenge, consultant provided additional potential solutions to the implementation challenge. Coders also noted timestamps for various activities to determine the amount of time spent on activities of note (e.g., amount of time providing performance feedback).

Five agencies completed all 12 consultation sessions, while one agency completed only 6/12 sessions before all clinicians withdrew from the study. One video recording was corrupted and was unable to be scored; thus, there was a total of 65 consultation sessions that could be coded. Coders needed to meet training criteria of 3 videos in a row with 80% of all items in exact agreement with the master coder. Monthly meetings with the coding team were held in which all members independently coded a video, and the group compared their scores to the master codes and discussed discrepancies. Coders were randomly assigned consultation sessions to score. Ten of the 65 sessions (15%) were rated by both raters to calculate inter-rater reliability. Intraclass correlations were as follows: Feedback = 0.99, Skill Rehearsal = 1.00, Case Support = 1.00.

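### Aim 2 pairs a three-component repeated-measures ANOVA with all 6 agencies, but one agency stopped after 6 of 12 sessions; the plan text also names no contrast for the Case Support prediction.

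*Combined protocol and SAP*

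**What the plan says.** The Aim 2 paragraph of the Data Analytic Plan gives the method: "Usability ratings were averaged for each consultation condition for each clinician and then examined using a repeated measures one-way ANOVA". On the sample it says: "Questionnaires from all 6 agencies were utilized for this analysis". It gives no rule for a clinician who lacks a mean for one component.

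Four other places bear on this.

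- *Design overview* describes the consultation phase as "three, 4-week blocks in which the group completed one consultation training activity per block".
- *Consultation phase* says "All providers received each of the 3 consultation conditions". On attendance it says "Consultation sessions were rescheduled for the following week if more than half of participants at an agency would not be present".
- *Data Collection for Questionnaires* says that the weekly forms asked about "perceptions on the usability of that week's consultation training activity".
- *Consultant Fidelity to Consultation Conditions* reports that "one agency completed only 6/12 sessions before all clinicians withdrew from the study".

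Specific Aim 2 predicts that Case Support will be seen as the most feasible, acceptable and appropriate component. *Statistical Analysis* says of the multilevel tools: "These tools were used to analyze results for Aims 1, 3, and 4". Aim 2 is not on that list.

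**The concern.** A one-way repeated-measures ANOVA, as usually run, needs all three component means from each clinician. An agency that left halfway through three single-component blocks cannot supply them. So the stated sample and the named method do not fit together, and a reader cannot tell how many clinicians or agencies stand behind each comparison.

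The second gap concerns the hypothesis. The F test asks only whether the three means differ. Its value does not change if the component labels are swapped, so a significant result is equally compatible with Case Support being rated lowest.

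**Working it through.** **1. Session count.** Five agencies with 12 sessions and one with 6 give 5 × 12 + 6 = 66. One recording was corrupted, so 66 − 1 = 65. This reproduces the plan's 65 coded sessions and confirms the premise.

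**2. What six sessions cover.** With blocks of four sessions and one component per block, 6 = 4 + 2 + 0. The third component was never delivered at that agency. Ratings concerned the current week's activity, so those clinicians have no mean for it.

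**3. Which component is missing.** The plan gives 20 coded Case Support and 22 coded Skill Rehearsal sessions, so Feedback is 65 − 20 − 22 = 23. Assume that each complete agency had 4/4/4, which gives 20 per component. Three patterns for the withdrawn agency then fit the counts:

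| Case Support | Skill Rehearsal | Feedback | Corrupted recording |
|---|---|---|---|
| 0 | 2 | 4 | Feedback |
| 0 | 3 | 3 | Skill Rehearsal |
| 1 | 2 | 3 | Case Support |

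Only the first respects strict four-session blocks, and it means that the agency had no Case Support.

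**4. Clinicians lost.** Groups had 3-5 clinicians, so five agencies hold 15-25. The Aim 1 text narrows this: 60 separate models over 5 outcomes is 60 / 5 = 12 clinicians in three agencies, taken here as all those enrolled there.

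- Withdrawn agency outside the Aim 1 three (suggested, not stated, by the requirement that effects replicate in all three): remaining 12 + 6 to 12 + 10 = 18-22; loss 3/25 = 12.0% to 5/23 = 21.7%.
- Withdrawn agency inside the Aim 1 three: total 12 + 9 to 12 + 15 = 21-27; remaining 21 − 5 to 27 − 3 = 16-24; loss 3/27 = 11.1% to 5/21 = 23.8%.

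These remaining counts assume no other missing ratings, so they are upper bounds.

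**5. Detectable difference.** Paired t test, two-sided 5%, 80% power, clinicians treated as independent, in SDs of the paired differences:

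- One contrast: 0.70 at n = 18 and 0.63 at n = 22.
- Both contrasts significant (simulated, equal true differences, equal and independent errors): power at those values is 68-69%. Reaching 80% needs about 0.79 at n = 18 and 0.70 at n = 22.

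**6. F test against contrasts.** Simulation with assumed means: Case Support and Feedback tied, Skill Rehearsal 10 points lower, residual SD 10 or 15, n = 18 or 22. F is significant in 49-92% of runs. A rule that needs both Case Support contrasts to be positive and significant claims Case Support as highest in 2.3-2.5%.

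**7. What the partial data could add.** Generalised least squares with 20 complete clinicians plus 4 who have only Feedback and Skill Rehearsal (4 per agency, 4 + 2 + 0 split), intraclass correlation 0.2-0.8, and the half-block mean at equal or double error variance. Keeping the partial agency lowers the standard errors of the Case Support contrasts by 1.6-3.5%, and that of Feedback versus Skill Rehearsal by 6.1-8.7%.

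**The case against.** The strongest reply is that the sentence on six agencies names a data source and does not claim that every clinician enters the F test. An unbalanced ANOVA with clinician and component terms also runs on partial data. With 20 complete clinicians and 4 lacking one mean there are 20 × 3 + 4 × 2 = 68 observations and 24 + 2 = 26 parameters, leaving 42 residual degrees of freedom. This stands in part. A reader might infer that no repeated-measures analysis could use six agencies; the documents do not support that, and the limit of five applies to the complete-case form. But the plan names no other form for Aim 2 and gives no exclusion rule, whereas Aims 1 and 4 do restrict themselves to agencies with sufficient data.

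A reader might also infer that the missing component is certainly Case Support. The counts show this only under strict four-session blocks and 4/4/4 elsewhere. In the third pattern the agency would have had all three components, though that departs from the blocks as described.

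Nor can one say that no contrast was tested. The analysis section calls itself an overview and refers model details to the Results section, which was not supplied.

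Finally, keeping or dropping the agency hardly changes precision for Case Support, and the withdrawal is openly reported. Both are true. They limit the harm but leave the stated sample and the sentence on receipt uncorrected.

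**Conclusion.** The point holds as an inconsistency between sample and method, with a false statement attached. With the blocks run as described, clinicians at one agency lack one of the three means, a complete-case repeated-measures ANOVA rests on at most five agencies, and not all providers received all three components. Confidence in this is high.

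Two parts are conditional. That the missing component is Case Support depends on strict blocks and equal counts elsewhere. That the prediction goes untested depends on the Results section adding nothing; on the plan text alone, F does not test it.

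The size is moderate: 3-5 clinicians, between 11% and 24% across both scenarios. Nothing here shows that the Aim 2 result is biased or invalid. There is also a limit on what any usability contrast can show. The prediction names feasibility, acceptability and appropriateness, while the scale yields one total usability score.

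**What to change.** 1. Report the number of clinicians and agencies contributing to each component. State either that the complete-case ANOVA rests on at most five agencies or, if an unbalanced or mixed-model form was used, name it.
2. Add two contrasts: Case Support minus Feedback, and Case Support minus Skill Rehearsal. Label them post hoc unless the Results section already has them. Say that Case Support is rated most usable only if both are positive and each is significant at two-sided 5%. Both must pass, so no alpha split is needed. Limit the conclusion to usability.
3. Correct the *Consultation phase* sentence to say that clinicians at the withdrawn agency did not receive all three components.
4. Optionally, as a sensitivity analysis, fit a mixed model with component effects and a clinician random intercept to all available means. State that it assumes missing at random, was chosen after data collection, treats clinicians within an agency as independent, and adds little precision for Case Support.

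Items 1 and 3 are wording and counts. Item 2 is two tests on ratings already collected. Its price is lower power than a single contrast has, as the working shows, and that should be stated beside the result.
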